adverse event reported. A blood sample will be obtained for RSV serology (20 mL) and (if applicable) clinical laboratory safety (10 mL). If a subject has delivered prior to the Day 14 visit, then the visit will be considered closed and no missed visit protocol deviation will be captured. The single exception is the blood draw for the clinical safety laboratory assessment [which only applies to subjects enrolled in the first year of study conduct in any country] that should be obtained at the Delivery visit.

Before subjects are released from the clinic, a replacement Study Identification Card will be offered to subjects, if needed, and the next visit will be scheduled. Subjects will also be reminded to contact the site to report the onset of labor, any severe or serious AE, any obstetrical complication, or symptom(s) suggestive of an RSV infection. The next visit will also be scheduled before subjects are released from the clinic.

Day 28 (± 2 days) – Telephone/Short Message Service (SMS) Contact, In-clinic, or Home Visit Safety Follow-up

Subjects who have not yet delivered will have a safety follow-up performed as either a telephone/SMS contact visit using an IRB/IEC-approved script (if applicable), an in-clinic visit, or a home visit. At this visit, whether conducted in in-clinic or at a home visit, study staff will assess the general health of the subject and query for any severe unsolicited AE, SAE, SNMC, MAE, clinical symptoms or signs of a suspected RSV illness, or any new obstetrical complication occurring since the last visit, and any concomitant medications taken for these events. Subjects participating in this visit via telephone or SMS and who report any severe or serious adverse event or symptoms suggestive of an RSV infection, may be asked to return to the clinic or schedule a home visit for evaluation of the event(s) to assess any effect(s) it may have on the pregnancy, and to potentially undergo a sampling of upper respiratory secretions for detection of respiratory viruses if symptom onset is within seven (7) days. The same procedures will be performed for subjects participating in this follow-up as an in-clinic or home visit, with the addition that a replacement Study Identification Card will be offered to all subjects (if needed) at the completion of this visit.

Delivery (D) – Hospital Follow-up Visit

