Subjects will be counselled to notify the obstetrician of the start of labor and will go to the registered hospital or delivery center for delivery. A venous blood sample (20 mL) for RSV serology should be obtained from the mother any time after hospital admission and optimally up to 12 hours post-delivery, which in extenuating circumstances (such as a delivery on a holiday or weekend), may be obtained up to 72 hours post-delivery. For applicable subjects (i.e., those enrolled in the first year of study conduct in any country) who deliver prior to the Day 14 visit, a venous blood sample (10 mL) for the clinical safety laboratory assessment should also be obtained. A cord blood sample (at least 5 mL) for RSV serology should be obtained by the obstetrician or designee immediately at the time of delivery. If cord blood is not obtained, then this information should be conveyed to the study staff responsible for the infant, so that infant sera may be collected in lieu of the cord blood (see [Infant Subject Study Visit](#) at the Delivery Day visit for details). The obstetrician or designee will also collect vital sign data at admission from the subject's medical chart and record all unsolicited adverse events experienced, and concomitant medications taken by, or administered to, the subject since the last visit. (*Note that routine medications for the management of labor and delivery do not need to be recorded.*) In addition, study staff will document the presence of perinatal management (including antibiotic therapy and any medical or surgical interventions for cause) and of any GBS screening result and treatment. Study staff will inform the infant's primary healthcare provider/pediatrician of the child's anticipated participation in the study before or immediately after delivery. A replacement Study Identification Card will be offered to all maternal subjects (as needed), and subjects will be reminded to contact study staff if symptoms suggestive of an RSV infection are experienced.

D+35 (± 7 days) – In-clinic or Home Post-delivery Follow-up Visit

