6.1.1.5 Day 14 (± 2 days) – In-clinic or Home Follow-up Visit

In addition to normal obstetrical follow-up including confirmation of fetal heart tones, all subjects will return to the clinic or will be evaluated by study staff at a home visit on Day 14 for the procedures listed below.

- Vital sign collection (heart rate, blood pressure, respiratory rate, and axillary body temperature).
- Query for any unsolicited AEs, MAEs, SNMCs, and SAEs occurring since the last study visit, and any concomitant medications taken for these events. *A physical exam may also be performed to evaluate any adverse event reported.* Subjects will also be queried regarding symptoms suggestive of RSV infection and, in the event onset is within seven (7) days, will undergo a sampling of upper respiratory secretions for detection of respiratory viruses (see **RSV Illness Surveillance** procedures in Section 6.2).
- Blood draw (10 mL) for post-vaccination clinical safety laboratory assessments (if applicable) and (20 mL) RSV serology. Subjects will be reminded to contact the site to report any severe or serious AE, obstetrical complication, or symptoms suggestive of an RSV infection.
- A replacement Study Identification Card will be offered to all subjects, as needed.
- Schedule the Day 28 visit.

If a subject delivers prior to the Day 14 visit, the procedures discussed above will not be performed and no missed Day 14 visit protocol deviation will be captured. The single exception is the blood draw for the clinical safety laboratory assessment [which only applies to subjects enrolled in the first year of study conduct in any country] that should be obtained at the Delivery visit.

6.1.1.6 Day 28 (± 2 days) – Telephone/SMS Contact, In-clinic or Home Visit Safety Follow-up

Subjects who have not yet delivered will have a safety follow-up performed as a telephone/SMS contact visit using an IRB/IEC-approved script (if applicable), an in-clinic visit, or a home visit. At this visit, whether conducted in-clinic or at home, study staff will assess the general health of the subject and query for any severe unsolicited AEs, SAEs, MAEs, SNMCs, clinical symptoms or signs of a suspected RSV illness, or any new obstetrical complications occurring

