8.1 Adverse Events

Adverse events (AEs) are defined as any unfavorable or unintended change in the physical, psychological, or biochemical condition of the subject. An AE temporally related to participation in the study or due to a procedure performed in the trial will be documented whether or not considered related to the test article. This definition includes intercurrent illnesses and injuries, and exacerbations of pre-existing conditions. Stable pre-existing conditions which do not change in nature or severity during the study are not considered AEs; however, these should be collected as part of the medical history. AEs will be considered treatment emergent from the date and time of the first administration of the investigational product.

Data concerning ALL adverse events will be collected at all scheduled visits for the entire study period for maternal subjects (i.e., from the time informed consent is obtained through post-delivery study Day 180) and through one year of life for infant subjects.

- In addition to the scheduled visits, maternal subjects will be encouraged to return to the clinic or notify the investigator if any severe (grade 3) local or systemic solicited AE occurs during the 7-day post-immunization period, or if a severe AE, a serious AE, or any other AE worrisome to the subject occurs at any time following vaccination.
- Parents/guardians will also be encouraged to report, or ask the infant's primary healthcare provider/pediatrician to report at any time, any other type of severe, serious, or otherwise concerning AE.
- If at a scheduled or unscheduled visit, symptoms are presented that would require a physical exam to adequately assess potential AEs, the exam should be performed and vital signs collected.

Adverse events will be recorded as observed by the investigator, designated personnel, or as provided by the maternal subject on the diary card or during a face-to-face visit with the maternal subject or the infant's parent/guardian. Full details of the AE (i.e., nature, date of onset and recovery as well as an assessment of severity, relationship to study agent, seriousness, treatment and outcome) will be recorded in the source documentation and captured in the eCRF

or entered into the eSource directly, and will generally require the investigator(s) causality assessment, except as discussed in subsequent sections.

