Appendix 1 – RSV-M-301 Study Procedures Schedule

Maternal Subject Study Procedures

Study Day:	-28 to 0	0	0-6	7 ^[1]	14 ^[1]	28 ^[1]	Delivery	D+35 ^[1]	D+180 ^[1]
Window (days):	--	--	--	+2	±2	±2	--	±7	±14
Approximate Week of Gestation:	24-36 ^{0/7}	28-36 ^{0/7}	28-36	29-37	30-38	32-40	--	--	--
Informed consent	x								
Medical history	x								
Physical exam	x								
Vital signs	x	x ^[5]		x	x		x ^[10]	x	x
Physical exam, if indicated		x		x	x		x	x	x
Ultrasound	x ^[2]								
Clinical safety phlebotomy	x ^[3]				x ^[3]		x ^[11]		
HIV, syphilis, HBV, and HCV testing (if applicable)	x ^[4]								
Pregnancy test									x
Fetal heart tones	x	x ^[5]		x	x				
Confirm eligibility		x							
Injection with recommended licensed vaccine dose	x ^[6]								
Injection with RSV F vaccine or placebo		x							
Diary card completed			x						
Diary card reviewed and collected				x					
Distribution of Study Identification Card ^[9]		x		x	x	x	x	x	
Memory aid distribution				x					
RSV serology phlebotomy	x				x		x ^[7]	x	x
Cord blood							x ^[8]		
RSV surveillance						Continuous			

Maternal Subject Study Procedures

Study Day:	-28 to 0	0	0-6	7^[1]	14^[1]	28^[1]	Delivery	D+35^[1]	D+180^[1]
Window (days):	--	--	--	+2	±2	±2	--	±7	±14
Approximate Week of Gestation:	24-36^{0/7}	28-36^{0/7}	28-36	29-37	30-38	32-40	--	--	--
AEs, MAEs, SNMCs, and SAEs query	x	x		x	x	x	x	x	x
Concomitant medications		x		x	x	x	x	x	x
Document perinatal management & GBS screening/treatment results	x						x		

- [1] Performed as a telephone or SMS contact visit (Day 28 only) using an IRB/IEC-approved script, if applicable, or as an in-clinic or home visit (Day 7, Day 14, D+35, and D+180) to monitor for safety. Depending on responses, maternal subjects participating via telephone or SMS contact or home visit, may be asked to return to the clinic or to schedule a home visit for further evaluation.
- [2] May be performed if subject does not have a prior second or third-trimester ultrasound that indicates there are no fetal anomalies.
- [3] To be performed at least two days prior to the planned Day 0 vaccination and on Day 14 in all subjects enrolled in the first year of study conduct in any country for serum chemistry (ALT, AST, total bilirubin, ALP, creatinine, and BUN) and hematology (hemoglobin, platelet count, and WBC count) assessments.

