12.4. Unsolicited Adverse Events

Any AEs reported by maternal subjects will be categorized as unsolicited events and Medical Dictionary for Regulatory Activities (MedDRA) coded by system organ class (SOC) and preferred term (PT). Solicited events with an onset after the solicitation period will also be classified as unsolicited AEs. Unsolicited events that occur within 7 days following vaccination should also be recorded in the subject diary. If any grade 3 unsolicited event is reported during this period, maternal subjects should be encouraged to contact the investigator by telephone. The investigator may request an *ad hoc* clinic visit at his/her judgment, and should enter any grade 3 unsolicited adverse event reported by telephone in the unsolicited AE eCRF promptly, even if the balance of diary data is not yet available. Continuing non-serious solicited AEs lasting beyond the 7-day diary period reported on the AE CRF to collect the symptom end date will not be summarized in the unsolicited AE tables. Solicited AEs reported on the AE CRF will be treated as solicited AEs and will be summarized in solicited AE tables only.

Any AEs reported in infants will be categorized as unsolicited events and MedDRA coded by SOC and PT. These can include, but are not limited to, abnormalities in vital signs, metabolic screening and developmental tests, neonatal hearing, congenital anomalies, respiratory failure, perinatal infections, neonatal death, complications that result in extended hospitalization; as well as any other SAE (as defined in Section 8.5 of the Protocol) or MAE or SNMC (as defined in Section 8.4 of the Protocol).

All unsolicited AEs will be assessed for severity and for causality for infants and maternal subjects.

The following summaries of unsolicited AEs will be presented for all maternal subjects in the Safety Population as part of the secondary analysis of safety:

- Overall summary of unsolicited AEs by treatment group (Day 0 post-vaccination to Day of delivery -1 and also Day 0 post-vaccination to Delivery +180).
- A summary by severity (mild, moderate, or severe), MedDRA SOC, PT, and treatment group (Day 0 post-vaccination to D+180).
- A summary by relationship to study vaccine, MedDRA SOC, PT, and treatment group (Day 0 post-vaccination to D+180).
- A summary of severe and related AEs, MedDRA SOC, PT, and treatment group (Day 0 post-vaccination to D+180).

For infants, the following summaries of unsolicited AEs will be presented:

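### The Day 28 maternal contact limits the unsolicited AE query to severe events, against Section 8.1 and the schedule, so the SAP 12.4 tables can under-count some non-severe events from about Day 14 to Day 28

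*Protocol*

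**What the plan says.** The Day 28 contact applies only to women still pregnant: "Subjects who have not yet delivered will have a safety follow-up performed". It may be by telephone or SMS, in clinic or at home. In the Synopsis staff assess general health and "query for any severe unsolicited AE, SAE, SNMC, MAE, clinical symptoms or signs of a suspected RSV illness", plus any new obstetrical complication. Section 6.1.1.6 has the same content: "query for any severe unsolicited AEs, SAEs, MAEs, SNMCs, clinical symptoms or signs of a suspected RSV illness". In both places the word *severe* qualifies the unsolicited AE item; the remaining items carry no severity limit.

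Two other parts of the protocol set no such limit. Section 8.1 states: "Data concerning ALL adverse events will be collected at all scheduled visits for the entire study period for maternal subjects". In Appendix 1 the row "AEs, MAEs, SNMCs, and SAEs query" is marked at Day 28 without qualification.

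The next scheduled maternal query is at Delivery. The Synopsis tells staff to "record all unsolicited adverse events experienced, and concomitant medications taken by, or administered to, the subject since the last visit". Section 6.1.1.7 also asks for all unsolicited AEs, but only back to the last clinic visit.

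SAP 12.4 plans an "Overall summary of unsolicited AEs by treatment group (Day 0 post-vaccination to Day of delivery -1 and also Day 0 post-vaccination to Delivery +180"). Its summaries by severity (mild, moderate, severe) and by relationship run from Day 0 to D+180. It does not mention that Day 28 used a different threshold.

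**The concern.** Day 28 is the only maternal visit with a severity threshold on unsolicited AEs, and no reason is given. Because the limit stands in both the Synopsis and the body, it cannot be put down to a single slip. A site that followed the Day 28 text, and then the Synopsis wording at Delivery, would not at any point actively ask about some non-severe events in a two-week stretch of pregnancy after vaccination.

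The percentage of women with unsolicited AEs is a maternal safety endpoint (Protocol 3.2.4.2) and part of the principal safety variable (SAP 12.1). A reader of the SAP 12.4 tables would assume that ascertainment was uniform from Day 0. If it was not, absolute percentages of non-severe events would be somewhat low and the severity distribution would shift slightly towards severe.

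**Working it through.** The plan gives no figure for this point, so the check is a comparison of texts followed by a day count.

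**Step 1. Scope of the unsolicited AE query at each maternal visit** (Synopsis and Sections 6.1.1.4 to 6.1.1.9)

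| Visit | Unsolicited AEs asked for |
|---|---|
| Day 7, Day 14 | any |
| Day 28 | severe only; SAEs, MAEs, SNMCs, suspected-RSV signs and new obstetrical complications at any severity |
| Delivery | all, back to the previous visit (Synopsis) or previous clinic visit (6.1.1.7) |
| D+35, D+180 | any |

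The events at risk are therefore non-severe AEs that were not medically attended and were not SNMCs, SAEs, RSV-related or obstetrical.

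**Step 2. Does the Delivery query cover Day 14 to Day 28?** The protocol treats even the telephone contact as a visit (Appendix 1, footnote 1: "Performed as a telephone or SMS contact visit (Day 28 only")). Reading each text literally:

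| How Day 28 was done | Synopsis wording at Delivery | Section 6.1.1.7 wording at Delivery |
|---|---|---|
| Telephone or SMS | not covered | covered |
| Home visit | not covered | covered |
| In clinic | not covered | not covered |

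The documents do not say how often each mode was used or which wording sites followed, so these cells cannot be weighted. Women who delivered before Day 28 had no Day 28 contact and are not affected.

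**Step 3. Size of the interval.** From Day 14 to Day 28 is 28 - 14 = 14 days. With the ±2-day windows on both visits it lies between 26 - 16 = 10 and 30 - 12 = 18 days.

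Share of antepartum follow-up = 14 / (delivery week - vaccination week, in days). Share of Day 0 to D+180 = 14 / (antepartum days + 180). Vaccination is allowed from 28 to 36 weeks. The delivery weeks are assumptions.

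| Vaccinated / delivered (weeks) | Antepartum days | Share before delivery | Share of Day 0 to D+180 |
|---|---|---|---|
| 28 / 39 | 11 × 7 = 77 | 14/77 = 18% | 14/257 = 5.4% |
| 33 / 39 | 6 × 7 = 42 | 14/42 = 33% | 14/222 = 6.3% |
| 36 / 40 | 4 × 7 = 28 | 14/28 = 50% | 14/208 = 6.7% |

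The last row is a boundary case: this woman delivers on Day 28 and may never have had the contact, so 50% should not be taken as typical.

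**Step 4. What these shares mean.** They are shares of follow-up time. If non-severe AEs occurred at a constant rate, they would bound from above the proportion of such events not asked about, because the classes in Step 1 were asked at any severity and Delivery may recover the rest. The documents give no AE rate for this interval, so no loss can be estimated.

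**The case against.** The strongest reply is that this is a wording inconsistency with no proven effect on data. The Day 28 text sets what staff ask, not what they record. They also assess general health, Section 8.1 still requires all AEs, and Section 8.2.2 treats any AE a woman reports as an unsolicited AE. Women have a memory aid from Day 7, and Delivery asks for all unsolicited AEs.

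Much of this stands, and it is why the under-count is possible rather than certain. It does not remove the point. The Day 14 reminder prompts women to call only about severe or serious AEs, obstetrical complications and RSV symptoms. The memory aid is optional and not collected. Recovery at Delivery depends on two texts that disagree.

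A reader might infer three stronger things that the documents do not support:

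- *That only severe events were sought at Day 28.* MAEs, SNMCs, SAEs, suspected-RSV signs and new obstetrical complications were asked at any severity.
- *That the comparison between arms is biased.* Both arms follow the same procedure under observer-blind conduct, and nothing in the text suggests different ascertainment by arm.
- *That power is lost.* AE analyses are descriptive percentages (Protocol 10.6, SAP 12.2). The 0.1% bound in Protocol 10.8 concerns SAEs, which Day 28 does ask about.

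The by-severity table is also less exposed than the pre-delivery one: it runs only from Day 0 to D+180, where the interval is 5-7%. Only the overall summary is cut at the day before delivery.

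**Conclusion.** The point holds as a contradiction with a limited, possible consequence. The Day 28 text in the Synopsis and Section 6.1.1.6 conflicts with Section 8.1 and the schedule, and the two Delivery look-backs conflict with each other. As a result, the SAP 12.4 tables can under-count, in both arms, non-severe AEs outside the separately queried classes with onset between about Day 14 and Day 28.

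The interval is about 18-33% of antepartum follow-up in typical cases and about 5-7% of Day 0 to D+180. This rests on delivery at 39 to 40 weeks and nominal visit days, and reading it as a bound on lost events also needs a constant event rate. Whether anything was lost depends on how Day 28 was conducted and which Delivery wording sites used, and the documents settle neither.

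**What to change.** 1. In the Synopsis and Section 6.1.1.6, delete *severe* so that Day 28 asks for all unsolicited AEs, as Section 8.1 and the schedule require.
2. Align the Delivery wording in the Synopsis and Section 6.1.1.7 so that the query covers all AEs since the last visit at which all AEs were asked.
3. For women already past Day 28, establish from the contact script and the CRF what was asked. Unless all AEs were asked, footnote the SAP 12.4 tables: non-severe AEs that were not medically attended, SNMCs, SAEs, RSV-related or obstetrical were not specifically queried at Day 28 and may be under-ascertained from Day 14 to Day 28.

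The Version 10.1 change history says all subjects were enrolled under Version 9 or earlier, and SAP Version 6.1 was approved in February 2019. Steps 1 and 2 will therefore reach few women, if any, and mainly put the record straight; step 3 is the useful one. The cost is protocol and script wording, a slightly longer Day 28 contact for anyone still to have one, one document check and one footnote.
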